#### 6.2.10. Period A: Day 70 (Procedures may be used as screening for eligible and consenting subjects for the open label extension study)

- Dosing compliance verification (Investigational product accountability and documentation) while subject is present to confirm reasons for missed/additional doses. **Based on blister card review and/or tablet count, any subject who is noted not to have taken at least 80% or has taken more than 120% of required doses at any scheduled visit during the study will be considered out of compliance and this must be recorded on the CRF and documented as a Medication Error on the CRF and the source documents.**
- Collect and review OFF time diary while subject is present.
- Review and assess adverse events (AEs).
- Assessment of concomitant medications.
- Perform full physical and neurological examination.
- Collect weight.
- Collect blood and urine for safety lab tests.
- Collect Prolactin laboratory sample.

- Perform standard supine triplicate 12-lead electrocardiogram (ECG).
- Perform standard single supine and standing vitals (HR and blood pressure).
- Perform the Columbia Suicidality Severity Rating Scale (C-SSRS) “Since last evaluation”.
- PK blood sample collection for PF-06649751 concentration. The time of sample collection and the date and time of the most recent dose of study medication prior to PK sampling should be recorded in the source documentation.
- Perform MDS-UPDRS Parts I, II, III, and IV.
- CCI [REDACTED].
- Perform Questionnaire for Impulsive-Compulsive Disorders in Parkinson’s Disease – Rating Scale (QUIP-RS).
- CCI [REDACTED].
- Dispense Investigational Product.
- Dispense OFF time diary and review instructions including requirement to complete diary for 3 consecutive days during Week 15.
- Instruct subject on continued daily dosing of PF-06649751 or placebo in accordance with randomized dose arm up-titration scheme (see [Table 2](#), Section 5.5.1, [Titration of PF-06649751](#)).
- Instruct subjects on continued adjunct stable L-Dopa (open-label) administration.

- Instruct subject to begin simultaneous adjunct down-titration of stable L-Dopa dose (refer to Section 5.5.3, [Period B:](#) ).

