An average daily OFF time (using 3 days recording the Hauser diary prior to the visit) will be calculated at all time points for each subject, which includes Baseline (prior to Day 0), Week 3, Week 5 and Week 10 (End of Period A), Week 13 (Period B; exists prior to Protocol Amendment 2 only) and also Week 15 (End of Period B). Change from baseline will then be calculated. Week 10 is the primary endpoint.

- Week 3 Hauser home diary data will be collected at the Week 3 visit for subjects randomized prior to Protocol Amendment 2, and at the Week 3 visit for subjects randomized under Protocol Amendment 2, where sites choose to perform an in-clinic visit (instead of a phone visit).
- Week 3 Hauser home diary data will be collected at Week 4 for subjects randomized under Protocol Amendment 2, when sites perform a phone visit for Week 3. The Week 3 phone visit will be used as the nominal visit.

In calculating the average daily OFF time, the following algorithms and rules are applied. (Rescue medication methods below are for all periods through Period A, and additionally Period B for subjects consented under Protocol Amendment 2 prior to entering Period B).

Valid Hauser Diary Days

1. Subjects who do not complete at least 12 awake hours of symptom diary data (not including ASLEEP time) will have that daily data set to missing (i.e. will not be considered as a valid symptom diary day). There will be no imputation of data for these diary days.
2. Any Hauser diary day on which rescue medication was used will NOT be considered a valid symptom diary day. The Hauser diary data reported on that day hereafter referred to as a rescue diary day, will not be used. As described more completely in the instruction for daily OFF time below, baseline data will be used to impute the observed response on these days. (All periods through Period A, and additionally Period B for subjects consented under Protocol Amendment 2 prior to entering Period B).

Entries at 30-minute Intervals (Only for subjects who have ≥ 12 awake hours of Hauser home diary data)

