7. The daily OFF time for every rescue diary day will be replaced by the subject's baseline OFF time, that is, the baseline 3-day average. (All periods through Period A, and additionally Period B for subjects consented under Protocol Amendment 2 prior to entering Period B).

Daily Average (Rescue diary days are for all periods through Period A, and additionally Period B for subjects consented under Protocol Amendment 2 prior to entering Period B)

8. Valid home diary days (at least 12 awake hours, after all imputation) and/or rescue diary days will be used to compute the average daily OFF time. The valid home or rescue diary day must be within 7 days of the clinic visit (or phone visit for Week 3 only as noted below or assigned to the closest planned visit as noted below) but not on or after the day of the clinic visit. If more than 3 valid home or rescue diary days are available, the 3 days closest to the clinic visit will be used.
 - Prior to Protocol Amendment 2, the three consecutive days before Day 0 could occur anytime during the screening period and was not restricted to within a week of the visit. Therefore, all home diaries before Day 0 will be considered for Baseline, with the 3 days closest to Day 0 being used for analysis.
 - Subjects, who have a phone visit for Week 3 and their home diary collected at Week 4, will use their Week 3 phone visit to determine within 7 days.
 - If a valid home or rescue diary is considered for exclusion based on the "within 7 days" rule, it will still be included if its nominal visit is equal to the closest planned visit, otherwise it will be excluded. Planned visits: Baseline (Day -1), Week 3 (Day 21), Week 5 (Day 35) or Week 10 (Day 70).
 - i. Example 1: A subject who completed Week 3 diaries on Days 8, 9, and 10 with the actual Week 3 visit occurring on Day 21. All diaries excluded as all Week 3 diaries would all have been closer to Baseline (Day -1) than Week 3 (Day 21).

- ii. Example 2: A subject who completed Week 10 diaries on Days 61, 62 and 63 with the actual Week 10 visit occurring on Day 70. All diaries included because the diaries are closest to Day 70 which matches the clinic visit (Week 10).
 - iii. Example 3: A subject who completed their Week 3 diaries on Days 11, 12 and 13 but the actual Day 21 visit occurred on Day 24. All diaries included because the diaries are closest to Day 21 which matches the clinic visit (Week 3).

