3.2. Secondary Endpoint(s)

Secondary endpoints evaluated during the entire double-blind period include:

- Daily OFF time (hours): change from baseline in average daily OFF time by Visit.
- Daily ON time with troublesome dyskinesia (hours): change from baseline in average daily ON time with troublesome dyskinesia by Visit.
- Daily ON time without troublesome dyskinesia (hours): the change from baseline in average daily ON time without troublesome dyskinesia (i.e. without dyskinesia or with non-troublesome dyskinesia, or alternatively “good time”) by Visit.

The same algorithm and rules employed for the calculation of OFF time will be used for the secondary variables. Baseline is defined using the 3 Hauser diary days prior to Day 0.

- MDS – Unified Parkinson’s Disease Rating Scale (MDS-UPDRS) Part III: Change from Baseline in MDS-UPDRS Part III Score by Visit.
- MDS-UPDRS Parts I, II, IV, and total score: Change from Baseline in the MDS-UPDRS Parts I, II, IV and Total Scores by visit.

The MDS-UPDRS will be collected at times specified in the STUDY PROCEDURES section of this protocol. *Although not required, every effort should be made to have the same individual perform the ratings for an individual subject throughout the course of the study.*

MDS-UPDRS Part III should be assessed consistently and approximately 2 to 4 hours following L-Dopa dose (except at screening).

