6. ANALYSES AND SUMMARIES

Both the FAS and PPAS populations will be used in the analyses of the primary efficacy endpoint, with the FAS being primary. For all other efficacy endpoints, only the FAS analysis set will be utilized.

For all efficacy analyses and summaries (Sections 6.1, 6.2, 6.3 {except CCI [REDACTED]} and 6.4): All data collected for subjects consented under Protocol Amendment 2 prior to entering Period B will be included for modelling and summaries. Otherwise, only data collected through Week 10 (Period A) will be included for subjects who do not meet the above condition, and their data collected after Week 10 will be in listings only.

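### SAP 3.1 rule 8 does not extend its closest-planned-visit rescue to Week 15, so any Week 15 diary day more than 7 days before the visit is excluded

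*SAP*

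**What the plan says.** The base rule in SAP 3.1, rule 8, is "The valid home or rescue diary day must be within 7 days of the clinic visit", and the day may not fall on or after the visit. A diary day that fails this gets a second chance: "it will still be included if its nominal visit is equal to the closest planned visit, otherwise it will be excluded". The visits that count are then listed: "Planned visits: Baseline (Day -1), Week 3 (Day 21), Week 5 (Day 35) or Week 10 (Day 70". Three worked examples follow, two for Week 3 and one for Week 10.

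Other parts of the plan put Week 15 in scope:

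- SAP 3.1 ends its list of time points for the average daily OFF time with "and also Week 15 (End of Period B). Change from baseline will then be calculated".
- SAP 3.2 carries the derivation over to the ON-time endpoints: "The same algorithm and rules employed for the calculation of OFF time will be used for the secondary variables".
- SAP 6 states: "All data collected for subjects consented under Protocol Amendment 2 prior to entering Period B will be included for modelling and summaries". Other subjects' data after Week 10 go to listings only.
- SAP 6.2.1 analyses the three diary endpoints at all visits by MMRM.
- Protocol 6.2.10 has the Day 70 visit "Dispense OFF time diary and review instructions including requirement to complete diary for 3 consecutive days during Week 15". The Schedule of Activities sets the Week 15 visit at Day 105 ±3.

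**The concern.** Week 15 is a defined time point of the diary algorithm, but it is missing from the list that decides whether an early diary can be kept. A Week 15 diary day outside the 7-day window is always nearest to some other listed visit, so it always fails the match.

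Two things are at stake. If no diary day remains, rule 11 sets the Week 15 average to missing. If exactly one remains, rule 10 averages that day with the last available week. For a subject with Week 10 data, half of the value labelled Week 15 then comes from Week 10, even when other Week 15 diary days were completed. The same diary pattern at Week 10 would have been used as recorded.

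**Working it through.** **Inputs.** The 7-day window, the rescue condition, the list of planned visits and the three examples come from SAP 3.1, rule 8. Rules 10 and 11 come from the same section. The visit windows come from the protocol's Schedule of Activities. SAP 3.4 equates Day -1 with the protocol's Day 0, so baseline is placed at 0.

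**Rule as applied.** For diary day *d* and visit day *v*, keep *d* if 1 ≤ *v* − *d* ≤ 7. Otherwise keep *d* only if the listed target day nearest to *d* (0, 21, 35 or 70) belongs to the visit for which the diary was recorded.

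**The SAP's examples reproduce.**

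- Example 1 (Days 8-10, Week 3 visit on Day 21): the days are 13, 12 and 11 days before the visit. Day 10 is 10 from baseline and 11 from Day 21, so it is nearer to baseline, as are Days 8 and 9. All are excluded, as stated.
- Example 2 (Days 61-63, Week 10 visit on Day 70): Day 63 is 7 days before the visit and already in the window. Days 61 and 62 are 9 and 8 from Day 70 and 26 and 27 from Day 35, so both are rescued. All are included, as stated.
- Example 3 (Days 11-13, Week 3 visit on Day 24): Day 11 is 10 from Day 21 and 11 from baseline. All three days are rescued, as stated.

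**The same patterns 35 days later, at Week 15.**

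- Days 96-98, visit Day 105: Day 98 is 105 − 98 = 7 days before the visit and is kept. Days 96 and 97 are 9 and 8 days before. Their nearest listed visit is Day 70 (distances 26 and 27), which is Week 10, so both are dropped. One day is left and rule 10 gives (Day 98 OFF time + last available weekly average) / 2. Example 2, the Week 10 counterpart, uses all three days.
- Days 98-100, visit Day 108: the days are 10, 9 and 8 days before the visit. Their nearest listed visit is again Day 70 (distances 28, 29 and 30), so all three are dropped and rule 11 sets Week 15 to missing. At Week 10, Days 63-65 with a Day 73 visit are also 10, 9 and 8 days before. They lie 7, 6 and 5 from Day 70, and all are kept.

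**All out-of-window days that the rescue can keep.**

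| Visit | Visit day | List as written | Week 15 (Day 105) added |
|---|---|---|---|
| Week 3 | 21 | Days 11-13 | unchanged |
| Week 3 | 24 | Days 11-16 | unchanged |
| Week 5 | 35 | none | unchanged |
| Week 5 | 38 | Days 29-30 | unchanged |
| Week 10 | 67 / 70 / 73 | Days 53-59 / 53-62 / 53-65 | unchanged |
| Week 15 | 102 / 105 / 108 | none / none / none | Days 88-94 / 88-97 / 88-100 |

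The midpoint between Days 70 and 105 is 87.5, which is why the rescue would start at Day 88. The midpoint between Days 35 and 70 is 52.5, which gives Day 53. With Day 105 added, Week 15 has 7, 10 and 13 rescuable days, the same as Week 10. As written, no Week 15 diary day is rescued for any visit day from 80 to 139.

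**The case against.** The strongest reply is that rule 8 computes nothing wrongly. The protocol asks for the diary in the week before the visit, and for Week 15 specifically during that week. A day recorded 8 or more days early usually departs from that instruction, and excluding it is the base rule. The rescue is an exception added in SAP version 3, and Week 15 simply falls back to the base rule. The version history also cites alignment with the first interim analysis plan for changes in Section 3.1. That might explain a list ending at Week 10, but the documents do not say so.

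Part of this stands: the fault is the uneven scope of the exception. But early days are not always the subject's departure. Days 98-100 lie in the week before the target Day 105, and a visit moved to Day 108 within its window puts all three outside the 7 days. No other provision recovers them, since the closest-visit rule in SAP 5.3 covers early termination visits only. Nothing says the omission is deliberate.

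Three stronger readings are tempting and are not supported:

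- A reader might infer that every other visit keeps what Week 15 loses. Week 5 rescues no day for a Day 35 visit and only Days 29-30 for a Day 38 visit, and Example 1 shows Week 3 diaries excluded.
- A reader might infer that the Week 15 copy of Example 2 is lost entirely. Day 98 is inside the window and is kept.
- A reader might infer that the primary endpoint is affected. No derived Week 10 value changes.

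**Conclusion.** The point holds as a gap in scope, and it is minor. As written, rule 8 can never keep a Week 15 diary day more than 7 days before the visit, although Week 15 averages are modelled for subjects who consented to Amendment 2 before Period B. The contrast is exact with Week 10, partial with Week 3 and almost absent with Week 5.

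The effect is confined to the Week 15 OFF-time endpoint and the two ON-time endpoints. Any influence on the Week 10 estimates could come only indirectly, through Week 15 values in the shared MMRM. Week 15 diaries within 7 days of the visit are untouched, and the rule does not depend on treatment arm. Leaving Week 13 off the list does no harm, because that diary visit existed only before Amendment 2 and those later data are listed, not modelled.

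The number of diaries affected is not stated and could be zero, so no loss of precision can be quantified. The conclusion rests on a literal reading of the list and on treating Day -1 as the protocol's Day 0, which reproduces all three examples.

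**What to change.** Before unblinding, add this entry to the planned visits in SAP 3.1, rule 8: *Week 15 (Day 105), for subjects who consented to Protocol Amendment 2 before starting Period B*. If the exclusion is intended, say so in one sentence with the reason.

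The cost is a few words in the SAP and one extra target day in the derivation program. The derived values at Weeks 3, 5 and 10 stay as they are. A fourth worked example, such as Days 98-100 with a Day 108 visit, would make the intended handling plain to the programmer.

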9. If only 2 valid home or rescue diary days are available prior to a visit, data from the 2 days will be used to calculate the average daily OFF time.
 10. If only one valid home or rescue diary day is available the average daily from the last available week will be averaged with the daily OFF time from the one valid diary day.
 11. Subjects that do not have any valid home diary days for a visit or who are completely missing a visit will have the average daily OFF time set to missing for that visit.

The extent of missing data will be evaluated as part of the Blind Data Review Meeting(s). Tabular displays will be developed to describe the extent of missing data.

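### SAP 3.1 rule 11 sets rescue-only diary visits to missing, while rules 7 to 10 give the same visits a value; no precedence is stated

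*SAP*

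**What the plan says.** The rules are in the numbered list in SAP 3.1. They apply through Period A, and in Period B for subjects who consented under Amendment 2 before entering it.

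- Rule 2: "Any Hauser diary day on which rescue medication was used will NOT be considered a valid symptom diary day". For such days, "baseline data will be used to impute the observed response on these days".
- Rule 7: "The daily OFF time for every rescue diary day will be replaced by the" subject's own baseline 3-day average.
- Rule 8: valid home days "and/or rescue diary days will be used to compute the average daily OFF time", so rescue days alone are enough.
- Rule 9 covers two usable days: "If only 2 valid home or rescue diary days are available prior to a visit", those two are averaged.
- Rule 10 covers one usable day: "If only one valid home or rescue diary day is available", it is averaged with the last available week.
- Rule 11: "Subjects that do not have any valid home diary days for a visit or who are completely missing a visit" have the visit average set to missing.

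SAP 5.3 and Appendix 1 then analyse observed cases without imputing a missing visit. SAP 6.1.1.1 only refers back to 3.1. SAP 3.2 extends the rules to the ON-time endpoints: "The same algorithm and rules employed for the calculation of OFF time will be used for the secondary variables".

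**The concern.** Rules 8 to 10 name two kinds of usable day, valid home days and rescue days. Rule 11 names only the first, and rule 2 has already said that a rescue day is not valid. A visit with at least one rescue day and no valid home day therefore meets the condition for receiving a value and the condition for being missing. Two programmers who each follow the SAP could produce different Week 10 data.

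The subjects affected are those the plan otherwise scores as having no benefit on rescue days. If they keep a value, they enter as zero change, or as a partly shrunken change when there is a lone rescue day. If they are missing, the MMRM in effect estimates their Week 10 result from their own earlier visits and their arm. The MMRM means feed the primary Bayesian Emax model (SAP 5.2.2.3.2), and criterion C1 is a fixed 1.5 h threshold on the point estimate.

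**Working it through.** **1. The same visit under each rule (no valid home day)**

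| Usable days at the visit | Rules 7 to 10 | Rule 11 |
|---|---|---|
| 3 rescue days | change = 0 | missing |
| 2 rescue days | change = 0 | missing |
| 1 rescue day | average of baseline and last available week, minus baseline | missing |

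Example for the last row: with a baseline of 6.0 h and a last available week of 4.0 h, the change is (6.0 + 4.0)/2 - 6.0 = -1.0 h. A visit with at least one valid home day is unaffected.

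**2. The plan's own figures**

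Protocol 9.1 gives SD 2.9 h, 32 evaluable subjects per arm, C1 (point estimate at least 1.5 h) and C2 (95% confidence that the effect is at least 0).

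- SE = 2.9 × √(2/32) = 0.725 h.
- C2 needs 1.645 × 0.725 = 1.19 h, which is below 1.5 h, so C1 governs.
- P(pass) = 1 - Φ((1.5 - δ)/0.725). This is 85.0% at δ = 2.25 h and 1.9% at δ = 0, matching the stated 85% and 2%.

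**3. Illustration of the two readings**

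Assumed mean changes are -1.0 h on placebo (the prior mean in SAP 5.2.2.3) and -1.0 - 2.25 = -3.25 h on active. Let qA and qP be the shares of subjects whose two or three usable Week 10 days are all rescue days. The documents give no rescue rate, so these shares are assumptions.

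- Rule 11, if the missing subjects resemble the rest of their arm: 3.25 - 1.0 = 2.25 h.
- Rules 7 to 9: 3.25 × (1 - qA) - 1.0 × (1 - qP).

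| Share | Both arms | Active only | Placebo only |
|---|---|---|---|
| 2% | 2.21 h | 2.19 h | 2.27 h |
| 5% | 2.14 h | 2.09 h | 2.30 h |
| 10% | 2.03 h | 1.93 h | 2.35 h |

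With SE held at 0.725 h, P(pass) under rules 7 to 9 is 81%, 79% and 87% at a 5% share, and 77%, 72% and 88% at 10%.

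The comparator under rule 11 is slightly below 85%, because dropped visits cost precision. At 10% in both arms, n = 28.8 per arm and SE = 2.9 × √(2/28.8) = 0.764 h, so P(pass) = 84%. At 10% in one arm it is also 84%.

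**4. If earlier visits already show rescue use**

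Assume that the Week 5 mean is 80% of the Week 10 mean, that k of 3 Week 5 days are rescue days, and that the Week 5 to Week 10 correlation is ρ. The gap (rule 11 minus rules 7 to 9) is then

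(3.25 qA - 1.0 qP) × (1 - 0.8 ρ k/3).

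With k = 2 and ρ = 0.6 the factor is 1 - 0.32 = 0.68. At 10% the gaps fall from 0.225, 0.325 and -0.10 h to 0.153, 0.221 and -0.068 h (both arms, active only, placebo only).

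**5. Lone rescue day**

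Take Week 5 as the last available week, again at 80% of the Week 10 mean and with no rescue days. Rule 10 then gives half of that, or 40% of the arm mean. At 10% in both arms the difference is 2.25 × (0.9 + 0.1 × 0.4) = 2.115 h, a gap of about 0.14 h from 2.25 h.

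**The case against.** The best defence is that the intended reading can be recovered from the list. Rules 8 to 10 run down through three, two and one usable days of either kind, and rule 11 is the natural zero-day case. Rule 10's closing words already call a home or rescue day simply valid, so the drafting is loose. This makes a slip likely. It does not remove the conflict, because rule 2 excludes rescue days from validity and being last in the list does not give rule 11 precedence.

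The reach may also be small. A single valid home day removes the problem. Background L-Dopa is meant to stay constant (protocol 5.8.3), although protocol 5.9 leaves rescue dose and frequency to the investigator. At a 1% share the gap is only 0.01 to 0.03 h.

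No bias in a fixed direction is shown. The sign reverses if rescue-only visits are confined to placebo. With no true effect and equal shares in both arms, both readings give zero difference, which is relevant to 1 mg, expected to have little or no effect (protocol 1.5.2). These limits on size and direction stand.

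The blind data review, the missing-diary summaries and the rescue-dose summaries (SAP 3.1, 5.3, 6.1.1.2 and 6.5.4) might expose the discrepancy, but none of them decides it. The interim analysis SAP is not among the documents, so how the rule was programmed is unknown.

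**Conclusion.** The concern holds. As written, SAP 3.1 both assigns a value to a rescue-only visit and sets it to missing, and neither 3.1, 5.3 nor 6.1.1.1 says which rule governs. That the conflict exists is certain from the text; its numerical effect is not known.

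Under the stated assumptions, a 10% rescue-only share moves the expected difference by 0.10 to 0.33 h, depending on the arm, or by about 0.07 to 0.22 h once earlier rescue use is allowed for. At 2% the shift is 0.02 to 0.07 h. These are pairwise approximations at the full 2.25 h design effect and do not refit the Bayesian Emax model. The point should be corrected because it governs a primary endpoint value and, through SAP 3.2, the ON-time secondary endpoints.

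**What to change.** In SAP 3.1 rule 11, insert *or rescue* after *valid home*, so that a visit is missing only when it has neither kind of day. Rescue-only visits then follow rules 7 to 10 throughout. Make the closing words of rule 10 match, so that the single day is described there too as a home or rescue day.

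The cost is a few words in the SAP, and a check that the diary derivation program and the interim analysis SAP agree with them, all before unblinding. No new data are needed. The estimated effect may be slightly less favourable if rescue-only visits occur on active treatment.
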